Secondary objective (s)	1. Barriers to unspecified kidney donation 2. Economic outcomes of unspecified kidney donation
Number of Subjects/Patients	(i) 16 - 24 participants (focus groups); (ii) 758 participants (questionnaires), as follows: Test group: 137 unspecified donors that proceed to donate and 243 unspecified donors that withdraw. Control group: 189 directed / specified donor controls that proceed to donate and 189 directed / specified potential donors who did not proceed; (iii) 45 participants (interviews)
Study Design	Prospective cohort study
Endpoints	(i) time from enquiry to donation (for those that proceed to donation) (ii) mental and physical health at 3 and 12 months post donation / withdrawal, compared to directed donor controls

Inclusion Criteria	Individuals contacting a UK transplant centre wishing to become specified or unspecified kidney donors or those that have already begun the work-up process
Exclusion Criteria	Foreign nationals that are unable to donate altruistically in their countries of residence or prisoners
Statistical Methodology and Analysis	Quantitative analysis: (i) Time-to-event analysis using Cox regression; (ii) propensity score weighted mean differences at 3 and 12 months using linear mixed effects models Qualitative analysis: Framework (thematic) approach

Glossary of Terms and Abbreviations

AE	Adverse Event
AR	Adverse Reaction
ASR	Annual Safety Report
CA	Competent Authority
CI	Chief Investigator
CRF	Case Report Form
CRO	Contract Research Organisation
DMC	Data Monitoring Committee
EC	European Commission
GAfREC	Governance Arrangements for NHS Research Ethics Committees
ICF	Informed Consent Form
ISRCTN	International Standard Randomised Controlled Trial Number
MA	Marketing Authorisation
MS	Member State
Main REC	Main Research Ethics Committee
NHS R&D	National Health Service Research & Development
PI	Principle Investigator
QA	Quality Assurance
QC	Quality Control
Participant	An individual who takes part in a clinical trial
RCT	Randomised Controlled Trial
REC	Research Ethics Committee
SAE	Serious Adverse Event

SDV	Source Document Verification
SOP	Standard Operating Procedure
SSA	Site Specific Assessment
TMG	Trial Management Group
TSC	Trial Steering Committee

1. Introduction

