2.4 Study Outline

2.5 Trial Statistics and Data Analysis

The study endpoints will be:

- i) time from enquiry to donation (for those that proceed to donation)
- ii) mental and physical health at 3 and 12 months post donation, compared to directed donor controls

All primary analyses will be undertaken by the study statistician and investigator / research fellow in accordance with a predetermined analysis plan.

Descriptive analysis will be used to describe the proportion of people who withdraw or proceed to donation, and the reasons for failing to proceed. The analysis will include all individuals enquiring about donation, with the dependent variable an indicator for each proceeding to donation. Centre-level structural and attitudinal factors identified in our

parallel study (IRAS 170483) will be included in the models to determine whether these variables explain variation in donation rates.

Descriptive analysis will be used to compare baseline variables for individuals that express an interest in donation that: i) the transplant team withdraw from donation; ii) those who decide not to proceed; iii) those that proceed to donation; and iv) the specified kidney donor control group, who either proceed or do not proceed to donate. Linear or logistic mixed-effects models will be used to estimate difference in outcome variables at the 3 and 12 months follow-up assessments between the groups at the outcome assessments. Group membership and follow-up assessment (time) will be included in the models as dummy variables. Interaction terms for group and time will allow for assessments of differences at individual time points. Models will adjust for potential demographic confounders measured at baseline (e.g. age, sex, education, ethnicity) and the baseline level of the outcome variable. Missing outcome data is under the assumption that data is missing at random. Sensitivity analysis will be performed to assess this assumption.

The analysis of qualitative data will be performed using the Framework (thematic) approach as described above.

3. Sample Size and Selection

Focus Groups

The two focus groups will recruit 8-12 potential or actual unspecified kidney donors each. These will be volunteers identified by UK transplant co-ordinators.

Questionnaires

Consecutive people contacting each of the transplant centres in the UK between September 2016 and October 2019 will be recruited to participate in the study.

Initial Recruitment Plan

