Individual and centre level predictors of time to donation will be based on cox regression models. Based on the expected sample size of 241 to February 2018 and a donation rate of 36%, it is anticipated that, accounting for the clustered nature of the data, the study will have 80% power to detect effects equivalent to a hazard ratio of 1.48 for a standardised continuous variable. Clustering is accounted for by a design effect assuming 12 observations per centre on average and intra-cluster correlation of .1. This compares with 80% power to detect a hazard ratio of approximately 1.33 based on the original target sample size and 1.40 based on the revised target. For all estimates the detectable hazard ratio is in the range considered 'small' when converting to Cohen's rules of thumb for interpretation. Increases in the overall sample size provide only negligible improvements in the detectable hazard ratio since the increasing number of observations per centre leads to diminishing returns beyond around 10 to 12 observations per centre.

[figure not shown]

Figure 1. Detectable hazard ratio given sample size (adjusted for the clustered nature of the data) assuming a 36% donation rate

Power with respect to outcomes compared to directed donors

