To address the issue of potential prolonged work-up time period for UKDs, donors will be asked to provide an estimate of the date of first contact with the transplant services. This will take place at the pre-transplant (Q2) time point. A second supplementary question will be asked at the first post-donation questionnaire (Q3, 3-months) asking donors to describe potential reasons for delays in their work-up process.

Due to a national decline in unspecified donor numbers and changes to the national allocation policy for unspecified donor kidneys, recruitment figures in April 2019 were below those forecasted. Permission was sought, and granted, by the study funder to extend the study recruitment period for a further 3 months (until 31st January 2020).

Consequently, the study's recruitment targets were changed as follows:

Interviews

Qualitative interviews will also be completed with a sample of 15 donors who completed their donation, 15 who withdrew and 15 who are withdrawn by the transplant team from the process. These individuals will be identified from the initial cohort of patients that approached transplant centres with the intention to donate altruistically.

Recruitment Targets

The following recruitment targets have been set:

Focus Groups: 2 focus groups of 8-12 previous donors and 8-12 non-donors.
Total: 16-24 participants

Interviews:

15 potential donors that donated
15 potential donors that did not donate (self-withdrawn)
15 potential donors that did not donate (withdrawn by clinical team)
Total: 45 participants

The following revised minimum recruitment targets have been set:

Questionnaires:

380 potential donors (test population)

- 137 who have donated
- 243 who did not donate

189 specified donors (control population 1) and 189 specified non-donors (control population 2)

Total: 758 participants

Inclusion criteria

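### Endpoint (i) is worded for donors only, while the Cox model that analyses it is powered on all prospective unspecified donors; the definition should match the analysis population

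*Protocol*

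**What the plan says.** Three places in the protocol bear on who is in the analysis.

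- **Synopsis.** The first endpoint is "i) time from enquiry to donation (for those that proceed to donation", and the first quantitative method is "i) Time-to-event analysis using Cox regression".
- **Section 2.5, Trial Statistics and Data Analysis.** The donors-only wording returns as the first of two study endpoints: "time from enquiry to donation (for those that proceed to donation". The same section then describes the analysis of donation: "The analysis will include all individuals enquiring about donation, with the dependent variable an indicator for each proceeding to donation". Centre-level factors from a parallel study "will be included in the models to determine whether these variables explain variation in donation rates".
- **Section 3, Precision and power with respect to donation rates.** "Individual and centre level predictors of time to donation will be based on cox regression models". The power statement reads "Based on the expected sample size of 241 to February 2018 and a donation rate of 36" per cent. It allows for 12 observations per centre and an intra-cluster correlation of 0.1, and arrives at 80% power for a hazard ratio of 1.48 per standard deviation. The corresponding figures are 1.40 at the revised target (380) and 1.33 at the original target (624). The precision of the overall donation rate is also worked out on all prospective donors.

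**The concern.** Hypothesis (i) asks why unspecified donation differs between regions, and the Cox model is the stated tool for individual and centre-level predictors. A candidate's path ends in donation, in self-withdrawal or in withdrawal by the clinical team. A model fitted only to those who donated selects on the outcome. Candidates who would have taken longest have had the most opportunity to withdraw, so a factor that pushes people out also strips slow cases from the donor set. The remaining donors then look faster, and a barrier can pass for a facilitator. About 64% of recruits are expected not to donate, so withdrawal is the more common outcome. Two analysts working from this protocol could fit models in different populations and report opposite directions for the same centre factor.

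**Working it through.** **1. Which population does the power calculation use?**

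Inputs from section 3: N = 241, 36% donating, 12 per centre, intra-cluster correlation 0.1, 80% power. The alpha level and sidedness are not stated for this calculation, so both 5% variants were tried.

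- Events: 0.36 × 241 = 86.8.
- Design effect: 1 + (12 − 1) × 0.1 = 2.1. Effective events: 86.8 / 2.1 = 41.3.
- Schoenfeld-type formula for a standardised covariate: HR = exp[(z_alpha + z_power) / √(effective events)].
- One-sided 5%: exp[(1.645 + 0.842) / √41.3] = 1.47, and power at 1.48 is 81%. The stated figure is reproduced.
- Two-sided 5%: 1.55, and power at 1.48 is 71%. It is not reproduced.
- At N = 380, one-sided, with 380/23 = 16.5 per centre: 1.404 against the stated 1.40.
- At N = 624 on the same basis: 1.37 against the stated 1.33, which was not matched.

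The risk set is visible in the inputs. A donors-only set would have a 100% event rate, not 36%. Twelve per centre gives 241/12 = 20 centres, close to the 23 in the UK; the 87 expected donors would fill only 87/12 = 7. Using a donors-only cluster size (87/23 = 3.8) gives 1.35 one-sided or 1.41 two-sided, not 1.48.

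The donation-rate precision agrees. With 1.96 × √(0.36 × 0.64 / N), the half-widths are 3.8%, 6.1% and 4.8% for N = 624, 241 and 380, against the stated 4%, 6% and 5%.

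**2. What would a donors-only Cox model estimate?**

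Only the 36% comes from the protocol; the constant hazards and the effect sizes below are assumptions. Scale the baseline hazards to 0.36 for donation and 0.64 for withdrawal, so that 36% donate. Under constant competing hazards, time to donation among donors is exponential with rate donation + withdrawal. If a factor multiplies the donation hazard by a and the withdrawal hazard by b:

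- P(donate) = 0.36a / (0.36a + 0.64b)
- donors-only HR = (0.36a + 0.64b) / (0.36 + 0.64)

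| a (donation) | b (withdrawal) | P(donate) | Donors-only HR |
|---|---|---|---|
| 1 | 2 | 22% | 1.64 |
| 1 | 1.5 | 27% | 1.32 |
| 0.8 | 2 | 18% | 1.57 |
| 0.8 | 1.5 | 23% | 1.25 |
| 0.67 | 2 | 16% | 1.52 |
| 0.67 | 1.5 | 20% | 1.20 |
| 0.8 | 1 | 31% | 0.93 |
| 0.67 | 1 | 27% | 0.88 |

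At a = 0.8 the sign reverses once b exceeds (1 − 0.288) / 0.64 = 1.11. At b = 1 the direction is right but the effect is shrunk.

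**3. Simulation check.**

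In 1,000 cohorts of 380 with a = 0.8 and b = 2, the donors-only fit gave a hazard ratio of about 1.59 and exceeded 1 in 98.5% of cohorts. The Cox model in all prospective donors, with withdrawals censored, gave about 0.79 (true value 0.80).

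**4. Does widening the risk set cost power?**

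No. Events are donations under either definition: about 87 of 241, or 137 of 380.

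**The case against.** The best reply is that the protocol already intends an analysis of everyone. Section 2.5 puts all enquirers and the centre factors into the donation models, and section 3 sizes the Cox model on all prospective donors. On that view the parenthesis says no more than that a donation time is observed only in people who donate. Barriers are also studied by other means: the recorded reasons for not proceeding, and interviews with 15 self-withdrawn and 15 team-withdrawn candidates. Censoring and competing-event rules normally belong in the analysis plan, which is not at hand.

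Most of this stands. A reader might infer that the barrier analysis, as planned, conditions on the outcome; the documents do not support that, because the surrounding text points to an all-enquirer intention. A reader might also infer that the yes/no indicator counts people still in work-up as non-donors, or that the recalled enquiry date added under the amendment, where "donors will be asked to provide an estimate of the date of first contact with the transplant services", is the Cox time origin. The protocol states neither, and Appendix 4 schedules a centre record of initial contact. The indicator and the Cox model of section 3 are compatible: one asks whether people donate, the other how fast.

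What the reply does not remove is that the endpoint is defined twice with an explicit population, and that this population differs from the one in the power calculation. This is a contradiction in stated text, not a detail left for later.

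**Conclusion.** The point holds as an inconsistency with a material consequence if the endpoint is taken at its word. The donors-only definition in the synopsis and section 2.5 cannot be squared with a Cox model powered at a 36% event rate in 241 or 380 prospective donors.

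The size is conditional. Where a barrier raises withdrawal by 50% to 100% and multiplies the donation hazard by 0.67 to 1.0, a donors-only model would give hazard ratios of 1.20 to 1.64 in the wrong direction. Where it leaves withdrawal alone and lowers the donation hazard, the result is 0.88 to 0.93 in place of 0.67 to 0.80. These figures rest on constant hazards and chosen effects, and show what could happen rather than what to expect. The contradiction itself needs no assumption.

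**What to change.** - Delete the parenthesis from endpoint (i) in the synopsis and in section 2.5.
- Define endpoint (i) in all recruited prospective unspecified donors: donation is the event, withdrawal (by the candidate or the clinical team) is a competing event, and those still in work-up at data cut are censored.
- Fit cause-specific Cox models for donation and for withdrawal. The second is needed because a factor acting only through withdrawal leaves the donation-specific hazard ratio at 1.
- Keep the donation-proportion analysis in all enquirers, since the overall and per-centre precision in section 3 is calculated for it. Keep time to donation among donors as a descriptive summary.

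The cost is a wording change and one additional model. The data are already scheduled: section 2.3 has withdrawals checked with coordinators every two weeks and classified by who initiated them. If the analysis plan already uses this risk set, only the protocol wording has to be aligned.

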Based on current trends we conservatively estimate that there will be at least 279 kidney transplants from unspecified altruistic donors during that period. Indeed, there were 107 UKD in the UK in 2013. Assuming that the proportion of individuals contacting transplant centres who go on to donate remains stable (36%, based on data from Portsmouth in 2012), we expect that 780 people considering unspecified altruistic donation will contact transplant centres during that period. Based on our previous retrospective study, we expect at least a 80% recruitment rate- that is, 624 in total, of which 224 will go on to donate). This recruitment rate is higher than is typical for longitudinal studies but justifiable given the population being studied. A sample size of 624 will provide sufficient precision to estimate the 95% confidence interval for proceeding to donation to within $\pm 4\%$ overall, and to within $\pm 18\%$ for each centre. In summary, we aim to recruit 224 who have undergone unspecified donation and 400 who failed to donate.

The control group will recruit 200 people who are donating to friend or relative (specified donors) and 200 individuals that intend to donate to a friend or relative but do not (specified non-donors). Based on our retrospective study we expect a recruitment rate of 80%. Therefore, we will need to approach 500 specified donors. Given a stable rate of approximately 1000 specified donations per year across the UK, we anticipate that we will be able to recruit the control group using the same three-year recruitment window as the main cohort. If there is no difference between the unspecified altruistic and specified donors on the physical and psychological variables at 12 months, it will be possible to determine that the lower limit of a one-sided 95% confidence interval will be above the non-inferiority limit of a standardised mean difference of 0.3, which is deemed to be the smallest acceptable clinically meaningful difference – this allows for 20% missing data due to drop-out, at a significance level of 5% with 90% power (14). These individuals will be recruited through transplant co-ordinators nationally.

Amended Recruitment Plan

An amendment was added to the protocol in December 2017, at the request of the Study Steering Committee and with the permission of the funder (NIHR). This was based on recruitment data to June 2017, and driven by a delayed study start and lower than expected recruitment rate.

Amendment

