Outcomes over time for undirected donors will be compared to directed donors. The hypothesis is that undirected donors do no worse than directed donors 12 months after follow-up in terms of mental and physical health. The original target sample size of 224 undirected donors and 200 directed donors provided 80% power to determine non-inferiority of outcomes with a non-inferiority limit equal to a standardised mean difference of no more than .27, which was rounded to .3 in the application and protocol. This allowed for 20% missing data at the 12-month follow up. Given the expected sample size of 87 undirected and 119 directed donors based on recruitment to February 2018, power for a non-inferiority test with the same limit is reduced to 68% assuming 20% missing data. The expected sample size has 80% power when the non-inferiority limit is set at a standardised mean difference of .38. The revised target of 137 prospective unspecified donors and 187 specified donors leads to has 80% power when the non-inferiority limit is set at a standardised mean difference of .32. The non-inferiority limit for the revised target sample size is more acceptable given that it is closer to the minimum important difference for the outcomes considered range between a standardised mean difference of between .3 to .4.

[figure not shown]

Figure 2. Power by non-inferiority limit (standardised mean difference) for original target sample size and expected sample size, accounting for 20% missing data at 12 months.

The revised power calculation with respect to outcomes for undirected compared to directed donors indicated revised target sample size would have 80% power to detect non-inferiority where the bound was a standardised mean difference of $d=.38$, as opposed the original bound of $d=.3$. For the SF12 physical component score (PCS) in undirected donors this relates to a difference of 3.3 units as opposed to 2.6 units; based on the standard deviation of the PCS for unspecified donors in the UK being 8.72 (Maple, H., et al., 2014. *Transplantation*, 98(11), pp.1182-1189.)

Amendment outcomes:

[figure not shown]
In summary, three main changes resulted from the amendment:

1. A reduction in the total recruitment and donation targets across all study populations
2. An extension to the recruitment period (to October 2019)
3. A change in primary focus from the 12-month to the 3-month outcomes data

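### The revised target is given two non-inferiority limits at 80% power, .32 and .38; only .32 reproduces, and the 3.3-unit PCS conversion rests on the other

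*Protocol*

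**What the plan says.** All of this is current text in Section 3 of the Protocol.

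- **Initial Recruitment Plan.** The decision rule is that "the lower limit of a one-sided 95% confidence interval will be above the non-inferiority limit of a standardised mean difference of 0.3". That value is described as the smallest acceptable clinically meaningful difference.
- **Power with respect to outcomes compared to directed donors, before Figure 2.** The original 224 and 200 donors had 80% power at .27, rounded to .3, allowing for 20% missing at 12 months. For the February 2018 projection of 87 and 119 donors: "The expected sample size has 80% power when the non-inferiority limit is set at a standardised mean difference of .38". The revised target of 137 and 187 donors "has 80% power when the non-inferiority limit is set at a standardised mean difference of .32".
- **Same subsection, after the Figure 2 caption.** The "revised target sample size would have 80% power to detect non-inferiority where the bound was a standardised mean difference of $d=.38". This is contrasted with the original bound of .3. Using a PCS standard deviation of 8.72, the pair "relates to a difference of 3.3 units as opposed to 2.6 units".

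The specified-donor target is 187 in the power paragraph and 189 in the recruitment targets; this makes no material difference below.

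**The concern.** One sample, with one missing-data allowance and one power level, cannot have two limits. The later statement repeats the value already given to the smaller, abandoned projection, and it carries the only PCS conversion offered for the revised sample.

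Hypothesis (ii) is a non-inferiority claim, so the limit decides whether it is met. The later paragraph sets .38 beside the original .3 and translates both into PCS units. A reader could take .38, or 3.3 units, as the margin now in force. An interval whose lower end falls between -0.38 and -0.32 would then pass under one sentence and fail under the other.

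**Working it through.** **Inputs.** One-sided 5% and zero true difference (Initial Recruitment Plan; the amendment restates neither). 20% missing at 12 months, sample sizes, limits and the PCS standard deviation of 8.72 (power subsection).

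**Formulas** (normal approximation, SD = 1, limit m):

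- SE = sqrt(1/(0.8 n1) + 1/(0.8 n2))
- limit at 80% power = (1.645 + 0.842) × SE
- power at limit m = Φ(m/SE − 1.645)

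**Step 1: reproduce the original figure.** For 224 and 200, SE = sqrt(1/179.2 + 1/160) = 0.1088 and the 80% limit is 2.487 × 0.1088 = 0.270. The Protocol says .27, so the method matches.

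**Step 2: revised target.** For 137 and 187, SE = sqrt(1/109.6 + 1/149.6) = 0.1257 and the 80% limit is 2.487 × 0.1257 = 0.313.

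- Power at .32: Φ(0.32/0.1257 − 1.645) = 81.6%
- Power at .38: Φ(0.38/0.1257 − 1.645) = 91.6%

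With 189 controls these become 0.312, 81.8% and 91.7%.

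**Step 3: superseded projection.** For 87 and 119, SE = sqrt(1/69.6 + 1/95.2) = 0.1577. The 80% limit is 0.392 and power at .38 is 77.8%. This is close to the stated .38, though not exact.

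| Sample (20% missing) | Stated limit at 80% power | Recomputed limit | Power at .32 | Power at .38 |
|---|---|---|---|---|
| 224 and 200 | .27 | 0.270 | 90.3% | 96.8% |
| 87 and 119 | .38 | 0.392 | 65.0% | 77.8% |
| 137 and 187 | .32 and .38 | 0.313 | 81.6% | 91.6% |

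**Step 4: can any other reading rescue .38 for the revised target?** One-sided 2.5% with 20% missing gives 85.6% power at .38. One-sided 5% with no missing data gives 95.9%, and one-sided 2.5% with none gives 92.2%. The limit for 90% power (one-sided 5%, 20% missing) is 0.368. None gives 80% at .38.

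**Step 5: PCS units.** 0.30 × 8.72 = 2.62; 0.32 × 8.72 = 2.79; 0.38 × 8.72 = 3.31. The stated 3.3 is the .38 value. The .32 limit is never converted; against it, 3.3 is about 0.5 units (19%) too wide.

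**Step 6: consequence if .38 were used as the margin.** For 137 and 189 with 20% missing, SE = 0.1255. With a true deficit of 0.30 SD, the probability of declaring non-inferiority is Φ((0.38 − 0.30)/0.1255 − 1.645) = Φ(−1.007) = 15.7%. Against a margin of 0.30 it is 5%.

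**Step 7: power at 0.30.** Φ(0.30/0.1255 − 1.645) = 77.2%, before any gain from adjusting for the baseline value of the outcome.

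**Side check.** For 87 and 119 the Protocol says "power for a non-inferiority test with the same limit is reduced to 68% assuming 20% missing data". With 20% missing, power is 60.2% at .30 and 52.7% at .27. With no missing data at .30 it is 68.5%.

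**The case against.** The strongest reply is that the .32 and .38 sentences only say where a given sample reaches 80% power; neither says that the analysis will use that limit. The Protocol's summary of what the amendment changed lists targets, recruitment period and a shift of focus to 3 months, not the limit. The only limit tied to a confidence-interval decision remains 0.3. Section 2.5 also refers to a predetermined analysis plan, which may fix the margin. This stands. A reader might infer that the amendment loosened the test, but the text shows ambiguity, not an adopted change, and the 16% figure is conditional on .38 being used.

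A reader might also infer that .38 exceeds what the Protocol regards as clinically important. The Initial Recruitment Plan supports that, but the power subsection puts the minimum important difference between .3 and .4, which contains .38. Nor is 3.3 the only PCS figure: 2.6 units is given for .3.

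On the 68% figure, the projection is abandoned, and the limit it refers to could be .27 or its rounded value .3. The match with the no-missing calculation at .3 is suggestive; it does not prove how the figure arose.

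None of this makes the .38 sentence correct for the revised target.

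**Conclusion.** The Protocol contradicts itself on the limit for the revised target, and the later statement is wrong as written. At that sample size 80% power corresponds to about .31 to .32 (about 2.8 PCS units). At .38 power is about 92%, and 3.3 units is not the conversion for this sample. The value .38 is the one stated for the superseded projection; that it was carried over is the likely explanation, not something the text says.

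This rests on a one-sided 5% level and zero true difference carrying over from the initial plan, on 20% missing data, and on an unadjusted comparison. The missing-data allowance is for 12 months, so these powers do not describe the 3-month comparison to which the amendment moves the primary focus. The target sample is unaffected; what is at stake is which number may be taken as the decision threshold for hypothesis (ii).

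**What to change.** 1. Correct or delete the paragraph after the Figure 2 caption. If kept, it should say that the revised target has 80% power at a limit of about .31 to .32, equivalent to about 2.8 PCS units at a standard deviation of 8.72.
2. State once which limit governs the analysis, in standardised and PCS units and with its matching power, before the outcome groups are compared. If it is the 0.30 of the Initial Recruitment Plan (2.6 PCS units), power at 137 and 189 with 20% missing is about 77% before baseline adjustment. If another limit is intended, say so and justify it against the two statements on the minimum important difference.
3. Correct or remove the 68% for the abandoned projection. With 20% missing it is 60% at .30 or 53% at .27, so name the limit used.

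The cost is wording only, with no new participants, visits or data. If 0.30 governs, the stated power falls from 80% to about 77%.
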